- n. An overnight fast is preferred; however, a minimum of a 6-hour fast is acceptable.
- o. Only collect if the Withdrawal visit occurs at Week 48, or 96.
- p. Blood sample for renal and bone biomarker assessments: **Renal:** Cystatin C; Retinol Binding Protein (RBP); **Bone:** bone specific alkaline phosphatase, procollagen type 1-N-propeptide, type 1 collagen cross-linked C-telopeptide, osteocalcin, 25 hydroxy-Vitamin D
- q. Whole blood/PBMC collection samples may be used for virologic analyses. PBMCs will be collected at Day 1, Week 96, and Withdrawal if prior to Week 96.
- r. Informed consent for genetic research must be obtained before sample collection
- s. One blood sample for CAB and RPV each to be collected at each PK timepoint. PK samples are to be collected pre-dose during visits requiring IM administration. 2-hour post dose samples also taken at Weeks 4b, 48, 56b, and 96. Pre-dose samples at Weeks 56b, 60, and 2 hour post-dose sample at Week 56b are only for subjects transitioning from Current Art arm to CAB LA + RPB LA. Pre-dose samples are to be collected after review of PK diary at Week 4b and 56b and prior to the final oral dose of CAB + RPV. Additionally, PK samples will be taken during the 1-week post-dose Week 5 and 41 visits. PK window allowed for sample collection; includes 3 to 10 days for 1-week post dose sample (Visits 5 and 41); ±one hour for 2-hour post dose sample (Weeks 4b, 48, 56b, and 96).
- t. Only for Participants entering CAB LA+ RPV LA Oral Treatment
- u. Participants switching to CAB LA + RPV LA will take final dose of oral lead-in regimen in the clinic at The Week 4b visit or Week 56b and begin injections. If possible, injections should be spaced approximately 2 cm from one another and from the site of any previous injection and or any injection site reaction. Bring RPV LA to approximately room temperature prior to injecting. Time and location of injection (right or left) as well as needle length used will be collected in the eCRF. The first injection can be performed as soon as central lab results become available and safety parameters are reviewed.
- v. With the exception of the NRS, all Patient Report Questionnaires/Surveys are recommended to be administered at the beginning of the visit before any other assessments are conducted and prior to administration of the NRS is to be given post injection. Conduct questionnaires/surveys at Withdrawal if occurring prior to Week 96.

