13.3.2. Definitions of Assessment Windows for Data Other than Health Outcome and PK

Table 9 Assessment Windows for Screening & Maintenance Phase Data

Parameters[d] collected in sparse visit [c]	Analysis Window	Target Study Day	Analysis Timepoint
	Study Day ≤ 1 (the first record if there are multiple values)	The day of earliest record	Screening
	Last available recorded value up to and	1	Baseline

Parameters[d] collected in sparse visit [c]	Analysis Window	Target Study Day	Analysis Timepoint
	including the date of first maintenance phase dose of IP		
ECG, CD8, CD4/CD8 ratio	2 ≤ Study Day ≤ 70	29	Week 4
	2 ≤ Study Day ≤ 42		
	43 ≤ Study Day ≤ 70	57	Week 8
	71 ≤ Study Day ≤ 98	85	Week 12
	99 ≤ Study Day ≤ 126	113	Week 16
	127 ≤ Study Day ≤ 154	141	Week 20
urinalysis, CD8, CD4/CD8 ratio	155 ≤ Study Day ≤ 210	169	Week 24
	155 ≤ Study Day ≤ 182		
	183 ≤ Study Day ≤ 210	197	Week 28
	211 ≤ Study Day ≤ 238	225	Week 32
	239 ≤ Study Day ≤ 266	253	Week 36
	267 ≤ Study Day ≤ 294	281	Week 40
	295 ≤ Study Day ≤ 322	309	Week 44
	ECG, CD8, CD4/CD8 ratio, urinalysis, lipids, bone and renal markers	323 ≤ Study Day ≤ 378	337
323 ≤ Study Day ≤ 350			
	For 'Current ART' arm; 351 ≤ Study Day ≤ Maintenance Current ART Stop Day ^[b] + 1 For 'Q4W' arm: 351 ≤ Study Day ≤ Max (Day of Last Q4W IM Dose + 35, Last Oral dose Day + 1) ^[a]	365	Week 52
	For subjects who discontinued from oral lead-in during Maintenance phase, Study Day > (Day of last oral lead-in dose+1) Subjects discontinued from Current ART and not continuing into extension phase Study Day > (Maintenance Current ART Stop Day ^[b] + 1)		Follow-up

[a] Last Q4W IM / last oral dose is only applied to subjects who permanently discontinue from study treatment

[b] Current ART stop day: the last permanently stop day among all ARTs taken during Maintenance phase.

[c] For parameters with sparse collection, post baseline data will only be slotted to those specific analysis windows. The Screening or Baseline slotting will be based on the same rules as all other lab parameters use.

[d] **Urinalysis:** Urine Albumin/Creatinine, Urine Creatinine, Urine pH, Urine Protein/Creatinine, Urine Erythrocytes, Urine Specific Gravity, Urine Leukocytes, Urine Retinol Binding Protein, Urine Phosphate, Urine Creatinine

Bone marker: Bone Specific Alkaline Phosphatase, Osteocalcin, Procollagen 1 N-Terminal Propeptide, Vitamin D, Type I C-Telopeptides

Renal marker: Cystatin C, Retinol Binding Protein

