13.6. Appendix 6: Derived and Transformed Data

13.6.1. General

Multiple Measurements at One Time Point

- If after window assignment there are multiple valid assessments of a parameter within the same window, then the following hierarchy will be used to determine the value to be used for summary statistics of observed values:
 - the assessment closest to the window target Study Day;
 - if there are multiple assessments equidistant from the target Study Day, then for continuous variables the mean of these values will be used and for categorical variables the worse assessment. For HIV-1 RNA, the geometric mean of the number of copies will be used as opposed to the arithmetic mean
- Assessments not chosen for use in summary statistics by this algorithm will still appear in the associated listings. Also, such valid assessments will be used when determining values of potential clinical concern for the 'any time On-treatment' time point, and for any algorithm that has specific rules for which observation to use (e.g., Snapshot).

Treatment Start Date

Treatment start date is defined as follows:
 
Maintenance Phase
 
 • For subjects randomised to Q4W IM, treatment start date is the date of oral lead-in of CAB+RPV entered onto the IP exposure CRF form when study treatment started. • For subjects randomised to Current ART, treatment start date is the date of the Day 1 visit. 
Extension Phase
 
 • For subjects randomised to Q4W IM, treatment start date is the date of Nominal Week 52 injection date. • For subjects randomised to Current ART, treatment start date is the start date of oral lead-in of CAB+RPV at Extension phase.
Study Day

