
The Study Day of an event (e.g., lab assessment, vital sign, ECG, start date of AE or HIV associated condition) will be derived as the number of days between the date of the event and the start date of study treatment on Maintenance phase as follows:
 
if date of event \geq start date of study treatment, then
 
 • Study Day = date of event - start date of treatment on Maintenance phase + 1 
if date of event < start date of study treatment, then
 
 • Study Day = date of event - start date of treatment on Maintenance phase 
Note that the start date of study treatment on Maintenance phase is considered to be on Study Day 1 and the day before this is Study Day -1; i.e., there is no Study Day 0.

Extension Phase Study Day

The Extension Phase Study Day of an event (e.g., lab assessment, vital sign, ECG, start date of AE or HIV associated condition) will be derived as the number of days between the date of the event and the initial start date of Extension phase IP as follows:
 
if date of event \geq start date of extension phase IP, then
 $\text{Extension Phase Study Day} = \text{date of event} - \text{start date of Extension phase IP} + 1$ 
if date of event < start date of Extension Phase IP, then
 $\text{Extension Phase Study Day} = \text{date of event} - \text{start date of Extension phase IP}$ 
Note that the start date of Extension phase IP is considered to be on Extension Phase Study Day 1 and the day before this is Extension Phase Study Day -1; i.e., there is no Extension Phase Study Day 0.

Long-Term Follow Up Study Day
The Long-Term Follow Up (LTFU) Study Day of an event (e.g., lab assessment, start date of AE or HIV associated condition) will be derived as the number of days between the date of the event and the end of IP treatment [i.e. $\max(\text{Last IM Injection Date}, \text{Last Oral Bridging End Date})$] as follows: If the onset of event falls in Long-term Follow up phase, then 
 • LTFU Study Day = date of event - end date of IP
Post-baseline

 • Post-baseline refers to the combined time phases of On-treatment and Post-treatment. Post-baseline may be further specified according to phase(s) of the study: Maintenance and Extension (for example, post-baseline across the maintenance and extension phases combined).
Study treatment/drugs

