
 Toxicities will be based on the Division of AIDS (DAIDS) grading system, Version 2.0, November 2014, as specified in the protocol of Appendix 12.2. Toxicity grades provided by the central laboratory do not distinguish between abnormally high or low criteria, when both are relevant for a particular parameter.

Laboratory Parameters

- When summarising toxicity grades for such parameters, they will be categorised as to whether they are above or below the midpoint of normal range.

Parameter	Below Midpoint for those \geq Grade 1	Above Midpoint for those \geq Grade 1
Fasted glucose	Hypoglycaemia	Hyperglycaemia
Sodium	Hyponatremia	Hypernatremia
Potassium	Hypokalaemia	Hyperkalaemia

National Cholesterol Education Program (NCEP) Lipid Categories

- In addition to DAIDS toxicity grades (see protocol), lipid values will be categorized according to the 2001 NCEP Adult Lipid Guidelines [Grundy, 2001]

Parameter	Value Range (mmol/L)	Value Range (mg/dL)	Category
Triglycerides	<1.70	<150	Normal
	1.70 to <2.26	150 to <200	Borderline High
	2.26 to <5.65	200 to <500	High
	\geq 5.65	\geq 500	Very High
Total Cholesterol	<5.18	<200	Desirable
	5.18 to <6.21	200 to <240	Borderline High
	\geq 6.21	\geq 240	High
HDL Cholesterol	<1.04	<40	Low
	1.04 to <1.56	40 to <60	Normal
	\geq 1.56	\geq 60	High
LDL Cholesterol	<2.59	<100	Optimal
	2.59 to <3.37	100 to <130	Near/Above Optimal
	3.37 to <4.14	130 to <160	Borderline High
	4.14 to <4.92	160 to <190	High
	\geq 4.92	\geq 190	Very High

Total Cholesterol / HDL Cholesterol Ratio

- When both total cholesterol and HDL cholesterol results are available from the same date for a subject, then the ratio will be calculated by dividing the total cholesterol result by the HDL cholesterol result. The ratio can be classified as follows:

Parameter	Value Range
Total Cholesterol / HDL Ratio	< 3.5
	3.5 to < 4.4
	4.4 to < 5
	\geq 5

Percentage change for lipids

The percentage change from baseline is calculated as:

$$\% \text{ change from baseline} = \frac{\text{value at Week 48} - \text{baseline value}}{\text{baseline value}} \times 100\%$$

Other Safety Endpoints
Columbia Suicide Severity Rating Scale (C-SSRS) (Posner, 2007)

 Missing data will not have any imputation performed (Nilsson, 2013)

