13.7.2.2. Handling of Missing data for Statistical Analysis

Element	Reporting Detail
Snapshot	
 In the Snapshot dataset, subjects without HIV-1 RNA data in the assessment window for the visit of interest (due to missing data or discontinuation of IP prior to the visit window) do not belong to 'HIV-1 RNA < 50 c/mL (or <200 c/mL)'. The nature of this missing data will be further classified in Snapshot summaries as either 'HIV-1 RNA ≥ 50' or 'No Virologic Data at Week X'; Appendix 11: Snapshot Algorithm Details for full details
LOCF	
 In the LOCF dataset, missing values will be carried forward from the previous, non-missing available on-treatment assessment. If the baseline value is missing any missing values until the first non-missing value will remain missing.
Lipid LOCF	
Baseline for Lipids LOCF Analyses:
 
 Last evaluable lipids assessment up to and including the start of IP, where 'evaluable' is defined as: Lipid modifying agents not taken within 12 weeks of the date of assessment and Lipids are collected in a fasting state. Subjects with unevaluable Baseline for Lipids (as defined above) will be excluded from this dataset.

Element	Reporting Detail
	
Post-Baseline:
 
 ● If subjects initiate serum lipid-lowering agents Post-baseline, then the last available fasted On-treatment lipid values prior to the initiation will be used in place of future, observed On-treatment values. ● Imputation at visits with observed on-treatment values will continue even if the subject discontinues the lipid-lowering agent. Missing assessments will not be imputed 
Analyses Evaluated with Lipid LOCF dataset:
 
This dataset will be used to summarize fasting lipids parameters in the following displays:
 
 ● Summary of Chemistry Values by visit ● Summary of Chemistry Change from Baseline by visit ● Summary of TC/HDL ratio Change from Baseline. ● All other displays of lipids (i.e. toxicity tables and NCEP tables) will use observed fasting data, without LOCF imputation

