3.70.	Safety	LB1	Summary of Urine Concentrations Changes from Baseline by Visit - xxx	CS Core (including renal biomarkers of Retinol Binding Protein, Albumin/creatinine, Protein/creatinine) (for 'WK48' report, XXX is 'Maintenance Phase'; For '96' and 'EOS' report, this table will be split into two: one with 'XXX' being 'Maintenance + Extension Phase for Q4W arm' , and one with 'XXX' being 'Extension Phase for Switching Population')	WK48, 96, EOS
3.71.	Safety	Shell TS4	Summary of Changes in Proteinuria Baseline Laboratory Result to Maximum Post-Baseline Laboratory Result - Maintenance Phase		WK48
Laboratory: NCEP Lipid and Biomarkers					
3.72.	Safety	Shell TS5	Summary of Changes in NCEP Fasting Lipid Baseline Category to Maximum Post-Baseline Category - Triglycerides - Maintenance Phase		WK48

CONFIDENTIAL

201585

Safety Tables (Displays will be for both treatment arms, unless specified)					
No.	Population	IDSL / TST ID / Example Shell	Title	Programming Notes	Deliverable [Priority]
3.73.	Safety	Shell TS5	Summary of Changes in NCEP Fasting Lipid Baseline Category to Maximum Post-Baseline Category – Total Cholesterol - Maintenance Phase		WK48
3.74.	Safety	Shell TS5	Summary of Changes in NCEP Fasting Lipid Baseline Category to Maximum Post-Baseline Category – HDL Cholesterol - Maintenance Phase		WK48
3.75.	Safety	Shell TS5	Summary of Changes in NCEP Fasting Lipid Baseline Category to Maximum Post-Baseline Category – LDL Cholesterol - Maintenance Phase		WK48
3.76.	Safety	Shell TS6	Summary of TC/HDL ratio Changes from Baseline - Maintenance Phase (LOCF Lipid)		WK48
3.77.	Safety	Shell TS7	Summary of Bone Markers Changes from Baseline at week 48		WK48,
3.78.	Safety	Shell TS7	Summary of Bone Markers values at Week 48		WK48,
3.79.	Safety	Shell TS8	Statistical Analysis of bone biomarkers (ratio of week 48 over baseline) - Observed Case		WK48
Laboratory: Hepatobiliary (Liver)					
3.80.	Safety	Liver1 /Shell TS11	Summary of Liver Monitoring/Stopping Event Reporting (Maintenance Phase)		WK48
3.81.	Safety	liver10/Shell TS12	Summary of Subjects Meeting Hepatobiliary Abnormality Criteria - Post-Baseline– Maintenance Phase		WK48
3.82.	Safety	liver10/Shell TS12	Summary of Subjects Meeting Hepatobiliary Abnormality Criteria - Post-Baseline– Maintenance +Extension Phase	(for Q4W arm only)	WK48, 96, EOS
3.83.	ESP	liver10/Shell TS12	Summary of Subjects Meeting Hepatobiliary Abnormality Criteria - Post-Baseline– Extension Phase	(for Current ART arm only)	WK48, 96, EOS

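### Table 3.74 summarises HDL by its maximum post-baseline category, which is the favourable end; this can matter only for participants with more than one post-baseline fasting HDL value

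*SAP*

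**What the plan says.** The safety table list in SAP Section 13.13.7 gives Tables 3.72 to 3.75 one title template and one mock shell (TS5), for triglycerides, total cholesterol, HDL and LDL in turn. The HDL entry, Table 3.74, reads "Summary of Changes in NCEP Fasting Lipid Baseline Category to Maximum Post-Baseline Category – HDL Cholesterol", is restricted to the Maintenance Phase, and has an empty programming note. Table 5 in Section 8.4 likewise places the NCEP lipid shifts under its maximum post-baseline columns without separating HDL.

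Section 13.6.3 says that "lipid values will be categorized according to the 2001 NCEP Adult Lipid Guidelines" and sets the cut-offs. Section 13.6.1 defines the period: "Post-baseline refers to the combined time phases of On-treatment and Post-treatment". On data source, Section 13.7.2.2 says "All other displays of lipids (i.e. toxicity tables and NCEP tables) will use observed fasting data, without LOCF imputation".

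**The concern.** In a safety shift table the post-baseline entry should be the participant's worst value, so that a transient deterioration is counted. The maximum does this for triglycerides, total cholesterol and LDL. For HDL the adverse end is Low, so the same word selects the best value. A participant who falls to Low at one fasting sample and is Normal or High at another would not appear as Low. The table would then err in one direction only, understating shifts into Low HDL. Fasting lipids have their own secondary objective in Section 2.2, so the direction of this display should be right.

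**Working it through.** The SAP states no numerical result for this display, so there is none to reproduce. The check has four steps.

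**1. Which end is adverse (Section 13.6.3)**

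| Lipid | Lowest category | Highest category | The maximum selects |
|---|---|---|---|
| Triglycerides | Normal | Very High | worst |
| Total cholesterol | Desirable | High | worst |
| LDL | Optimal | Very High | worst |
| HDL | Low (<40 mg/dL) | High (≥60 mg/dL) | best |

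The SAP's own Framingham equation (Section 13.6.2) agrees. The coefficient of log(HDL) is −0.70833 in females and −0.93263 in males. Raising HDL from 40 to 60 mg/dL multiplies the risk term by exp(b × ln(60/40)):

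- females: exp(−0.70833 × ln 1.5) = 0.75
- males: exp(−0.93263 × ln 1.5) = 0.69

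Higher HDL means lower predicted risk.

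**2. Whether another rule reverses the direction**

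- Section 13.6.1 says "for continuous variables the mean of these values will be used and for categorical variables the worse assessment", but this applies only to assessments equidistant from a target day within one window.
- Section 13.6.3 says of two-directional toxicity grades that "they will be categorised as to whether they are above or below the midpoint of normal range", and tabulates glucose, sodium and potassium, not HDL.
- Section 13.7.2.2 fixes only the data source for the NCEP tables.
- Table 5 and the programming note for Table 3.74 give no exception.

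**3. When maximum and minimum can differ**

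- In Table 9 (Section 13.3.2) lipids have one post-baseline Maintenance window, Week 48, Days 323 to 378. Its note on sparsely collected parameters says "post baseline data will only be slotted to those specific analysis windows".
- For fasting laboratory tests at withdrawal, the schedule in Section 13.2.1 says "Only collect if the Withdrawal visit occurs at Week 48, or 96".
- No values are carried forward in the NCEP tables.

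The schedule therefore gives one value per participant, for which the maximum equals the minimum and the difference is 0. A second value must come from an unscheduled or repeat fasting sample, which Section 13.3.1 admits to summaries spanning the whole on-treatment period. The two values must also lie in different categories. Example: HDL of 38 and 45 mg/dL is Normal by the maximum and Low by the minimum.

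**4. Illustration for participants who have more than one value**

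The inputs are assumptions, not SAP figures: normally distributed HDL with mean 45 to 55, between-person SD 13 and within-person SD 3 to 5 mg/dL.

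| Post-baseline values per participant | Maximum and minimum categories differ |
|---|---|
| 1 | 0% |
| 2 | 15% to 25% |
| 3 | 22% to 38% |

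At mean 50 and within-person SD 5, with two values, 29.7% are Low by the minimum and 17.2% by the maximum. These rates apply only to participants with that many samples. They do not measure the effect on the whole table, because the SAP does not give the share of participants with repeat samples.

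**The case against.** The strongest reply is that the planned data make the point empty: with one scheduled lipid draw in Maintenance, maximum and minimum agree. Even a repeat sample inside the Week 48 window drops out if the closest-to-target rule in Section 13.3.6 is applied before the maximum. This stands as a limit on size. It is not a complete answer, because Section 13.3.6 itself exempts whole-period displays and algorithms with their own selection rule. If the closest-to-target rule does come first, the word maximum has no function.

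A second reply is that the derivation may sit in Shell TS5, which is in a separate document. That also stands as a limit: if TS5 takes the worst HDL category, the fault is only in the title. The title would still misdescribe the table.

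A third reply is that HDL is shown elsewhere. Figure 3.15 plots HDL categories at Week 48 against baseline with no maximum, and separately from the other three lipids in Figure 3.14. Tables 3.55, 3.58, 3.59 and 3.76 also carry HDL information. A Low value at Week 48 would therefore be visible in Figure 3.15. But that figure shows a single visit and does not correct the shift table.

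Finally, pooling all Maintenance Phase fasting values could be called a separate choice. It keeps the scope that the title, read with the SAP's definition of post-baseline, already implies.

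**Conclusion.** The concern holds as a minor point. As written, Table 3.74 takes the most favourable HDL category while its three companion tables take the worst, and nothing in the SAP corrects this. The effect is nil for anyone with only the scheduled Week 48 sample, and nil throughout if the closest-to-target rule is applied first. Otherwise it is confined to participants with at least two post-baseline Maintenance fasting HDL values in different categories, a number the SAP does not give. The table is descriptive, and the change-from-baseline lipid endpoint is served by Tables 3.55 and 3.58. The conclusion rests on the SAP text alone, since Shell TS5 could not be read.

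**What to change.** Derive Table 3.74 on the minimum (worst) post-baseline NCEP category for HDL, taken across all post-baseline fasting values in the Maintenance Phase, and retitle it to say so. Leave Tables 3.72, 3.73 and 3.75 on the maximum. Add a footnote to Table 5 recording the HDL exception, and check that Shell TS5 agrees. The cost is one title, one line of programming and one footnote.

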13.13.8. Safety Figures

Safety : Figures					
No.	Population	IDSL / TST ID / Example Shell	Title	Programming Notes	Deliverable [Priority]
Adverse Events					
3.1.	Safety	AE10	Plot of Common Adverse Events and Relative Risk-Q4W vs Current ART at Maintenance Phase	CS CORE	HL, WK 48
3.2.	Safety	LIVER9	Scatter Plot of Maximum vs. Baseline for ALT (Maintenance Phase)	CS CORE	HL, WK 48
3.3.	Safety	LIVER9	Scatter Plot of Maximum ALT vs. Maximum Total Bilirubin (Maintenance Phase)	CS CORE	HL, WK 48
3.4.	Safety	Shell FS2/	Matrix Plot of Maximum Liver Chemistries at Maintenance Phase	CS CORE	HL, WK 48
3.5.	Safety	Shell FS3/	Plot of Onset, Duration, and Severity of Overall and Common Maintenance Phase Injection Site Reaction AEs by Maximum Grade: CAB/RPV		WK 48
3.6.	Safety	Shell FS3/	Plot of Onset, Duration, and Severity of Overall and Common Maintenance Phase Injection Site Reaction AEs by Maximum Grade: CAB		WK 48
3.7.	Safety	Shell FS3/	Plot of Onset, Duration, and Severity of Overall and Common Maintenance Phase Injection Site Reaction AEs by Maximum Grade: RPV		WK 48
3.8.	Safety	Shell FS4/	Plot of Incidence of Maintenance Phase Injection Site Reaction Adverse Events-Overall and Common – CAB/RPV		WK 48
3.9.	Safety	Shell FS4/	Plot of Incidence of Maintenance Phase Injection Site Reaction Adverse Events-Overall and Common – CAB		WK 48
3.10.	Safety	Shell FS4/	Plot of Incidence of Maintenance Phase Injection Site Reaction Adverse Events-Overall and Common – RPV		WK 48
3.11.	Safety	Shell FS4/	Plot of Incidence of Grade 3-5 Maintenance Phase Injection Site Reaction Adverse Events - Overall and Common - CAB/RPV		WK 48

Safety : Figures					
No.	Population	IDSL / TST ID / Example Shell	Title	Programming Notes	Deliverable [Priority]
3.12.	Safety	Shell FS4/	Plot of Incidence of Grade 3-5 Maintenance Phase Injection Site Reaction Adverse Events - Overall and Common - CAB		WK 48
3.13.	Safety	Shell FS4/	Plot of Incidence of Grade 3-5 Maintenance Phase Injection Site Reaction Adverse Events - Overall and Common - RPV		WK 48
3.14.	Safety	Shell FS1	Bar Chart of Fasting LIPID NCEP Categories for Triglycerides, Total Cholesterol, and LDL at Week 48 vs. Baseline	Example: arenv/arprod/gsk3365791/mid_dori_ph3/week48/outputs/figure 3.062	WK 48
3.15.	Safety	Shell FS1	Bar Chart of Fasting LIPID NCEP Categories for HDL at Week 48 vs. Baseline		WK 48

